6. MILESTONES

Milestones	Planned Date		
Start of data collection	Two months after protocol approval		
End of data collection	When data through SEP2015 become available for analysis (estimated as 4Q2016)		
<registration eu="" in="" pas="" register="" the=""></registration>	Before the start of the study		
Final report of study results*	Twelve months after the end of data collection		
*Timing of final report includes the following:			
Data analysis: Three months after data are available			
Final tables available: Two months after data analysis is complete			
Report writing: Three months			
Report review (full Consortium): Four months			

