8.2. Secondary Objectives

To estimate the overall proportion of domperidone prescriptions before and after implementation of the risk minimisation measures for domperidone for each of the components of the composite endpoint individually, the time trend of apparent indication, and days supplied (\leq 7 days vs. >7 days), and the age and sex of the people receiving prescriptions.

9. **RESEARCH METHODS**

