9.2. Setting and Study Population

9.2.1. Study Setting and Population

The study population will be defined as all patients receiving domperidone in the outpatient setting during the pre-defined periods (pre- and post- implementation periods of the risk minimisation activity) in the selected European Union countries (France, Germany, United Kingdom, Belgium, and Spain). Patients will be included in the study cohort if they have at least 1 prescription for domperidone in the selected databases during the pre-defined periods, and have membership or have been registered with the practice and have available medical history for at least 180 days before the domperidone prescription.

The date of the first prescription of domperidone in the pre-defined study periods will be defined as the index date. Patients will be followed from the index date to the earliest of the following dates:

- end of the study period;
- transfer out of the practice; or
- end of the practice's qualification as up to standard (a designation used in some databases to differentiate between practices that meet a data standard and those who do not for databases, such as CPRD).

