9.2.2. Study Period

The study period will be divided into a background period and pre- and post- implementation periods of risk minimisation measures as follows:

- A background period (1 January 2011 through 31 March 2013)
- A 1-year pre-implementation period of risk minimisation measures (1 April 2013 through 31 March 2014)
- A 1-year post-implementation period of risk minimisation measures (1 October 2014 through 30 September 2015)

The period during which the label change took place and the DHPC was sent will be used as the period during which the risk minimisation measures were implemented (1 April 2014 through 30 September 2014).

Because the amendments to the product information were suggested by the PhVWP in October 2011, the study will track prescribing pattern changes from 1 January 2011 (a time that preceded most of the discussion and implementation of the label changes, i.e., a background period) through 30 September 2015.

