9.3.4. Use in Patients with Contraindicated Conditions

The contraindication for moderate or severe hepatic impairment will be identified by any diagnosis of hepatic cirrhosis, hepatic failure, or hepatic coma, between 1 January 2011 and 1 day before the prescription was written. The cardiac contraindication will be identified by a diagnosis of QTc prolongation, ventricular arrhythmia, or congestive heart failure in the 6 months before the prescription was written, or a diagnosis of hypokalemia in the 30 days before the prescription was written.

9.3.5. Concurrent Use with Drugs that Prolong the QT Interval or are Potent CYP3A4 Inhibitors

Domperidone is used as needed, therefore the duration of use may not be the same as the number of days for which domperidone is supplied. As a result, duration of use will be assessed under the following 2 scenarios, which will be likely to bracket the actual (but unknown) situation:

- 1. Domperidone is used only for as little as 1 dose after it is prescribed, and
- 2. Domperidone is used for the entire number of days supplied.

For the first scenario, the assessment of concurrent use with contraindicated medications will focus on drugs that were prescribed before or on the date of the domperidone prescription and whose duration of use includes the date of the domperidone prescription. For the second

scenario, assessment of concurrent use with contraindicated medications will also include drugs that were prescribed during the days' supply of the domperidone prescription.

A list of drugs that are known to prolong the QT interval is provided in Annex 3 and those that are potent or strong CYP3A4 inhibitors appear in Annex 4.

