9.7. Data Analysis

Data analysis in the study will be descriptive. Continuous variables will be presented using appropriate descriptive statistics, such as mean, median, standard deviation and range. Categorical variables will be presented using percent and frequency tables. The rates and 95% CI of all study endpoints (i.e., risk minimisation indicators) will be calculated for the 2011-2015 period, using quarterly time blocks for the pre- and post- risk minimisation implementation periods. The rates will be calculated per 1000 domperidone-treated patients or as percentage of domperidone prescriptions, as appropriate. Paediatric data will be described separately from adult patients and rate of paediatric use will be calculated as fraction of overall domperidone utilisation. Missing values will be reported as missing and no imputation will be undertaken. All data analysis will be done in SAS using the version that is current when the analyses are done.

The rates for the primary endpoints of the study (the proportion of all prescriptions that are consistent with the revised label) will be calculated 4 ways to address uncertainty about 1) Unknown indication (is it assumed to be nausea and vomiting and therefore on-label, or is it assumed to be some other indication and therefore off-label) and 2) Duration of use that may be shorter than the days' supply (prescriptions with more than 7 days' supply assumed to

be intended for ≤ 7 days use, and provision of additional tablets for possible future episodes, and therefore on-label, versus assumed to be for >7 days use and therefore off –label):

- 1. Unknown indication assumed to be nausea and vomiting. Duration assumed to be ≤ 7 days (most optimistic scenario) meets the following conditions:
 - a. Prescription for nausea and vomiting or unknown indication but no recent diagnosis of GERD, gastroparesis, IBS, symptoms of postural hypotension in Parkinson patients, or as an aid to lactation;
 - b. Dose no higher than recommended;
 - c. No prescription to patients with certain cardiac and hepatic conditions; and
 - d. No co-prescription with CYP3A4 inhibitors or QT-prolonging drugs. (This considers such contraindicated co-medications only when they were prescribed ≤ the date of the domperidone prescription.)
- 2. Unknown indication assumed to be an off-label indication, duration assumed to be \leq 7days (an intermediate scenario) meets the following conditions:

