 - Prescription for nausea and vomiting but no recent diagnosis of GERD, gastroparesis, IBS, symptoms of postural hypotension in Parkinson patients, or as an aid to lactation. Unknown indication will be assumed to be off-label (This differs from #1 above);
 - b. Dose no higher than recommended;
 - c. No prescription to patients with certain cardiac and hepatic conditions; and
 - d. No co-prescription with CYP3A4 inhibitors or QT-prolonging drugs (This considers such contraindicated co-medications only when they were prescribed ≤ the date of the domperidone prescription)
- 3. Unknown indication assumed to be nausea and vomiting, duration assumed to be the days' supply (an intermediate scenario) meets the following conditions:
 - Prescription for nausea and vomiting or for unknown indication but no recent diagnosis of GERD, gastroparesis, IBS, symptoms of postural hypotension in Parkinson patients, or as an aid to lactation (This is the same as in #1 above);
 - b. Duration (days' supply) ≤7 (This differs from #1 above and from #2 above, which don't examine days' supply)
 - c. Dose no higher than recommended;
 - d. No prescription to patients with certain cardiac and hepatic conditions; and

- e. No co-prescription with CYP3A4 inhibitors or QT-prolonging drugs. (Considers such contraindicated co-medications when prescribed ≤ the date of the domperidone prescription or prescribed within the days potentially covered by the domperidone prescription).
- 4. Unknown indication assumed to be an off-label indication, duration assumed to be the days' supply (most pessimistic scenario)
 - Prescription for nausea and vomiting but no recent diagnosis of GERD, gastroparesis, IBS, symptoms of postural hypotension in Parkinson patients or as an aid to lactation; Unknown indication assumed to be off-label (This differs from #1 above)
 - b. Duration (days' supply) ≤7 (This differs from #1 above and from #2 above, which don't examine days' supply.)
 - c. Dose no higher than recommended;
 - d. No prescription to patients with certain cardiac and hepatic conditions; and
 - e. No co-prescription with CYP3A4 inhibitors or QT-prolonging drugs. (Considers such contraindicated co-medications when prescribed ≤ the date of the domperidone prescription or prescribed within the days potentially covered by the domperidone prescription).

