Rates of the study endpoints will be assessed for the pre-implementation period (1 April2013 through 31 March2014) and will be compared with the 1-year post-implementation period (1 October2014 through 31 March2015). In addition, each of the above label requirements that contribute to the primary endpoint will be compared for the same two 1-year periods.

In addition:

- The apparent indications, and the days supplied (≤7 days vs. >7 days) will be tabulated.
- 2. There will be a table showing the demographic characteristics, of the study population (sex, age group).

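### Data ending on 30 September 2015 cut the scenario-2 co-medication window for late post-period prescriptions only, slightly understating post-period concurrent use

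*Protocol*

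**What the plan says.** Section 9.3.5 assesses concurrent use with QT-prolonging drugs or potent CYP3A4 inhibitors under two scenarios. Scenario 1 looks at the domperidone prescription date and backwards. Scenario 2 adds a forward part: "scenario, assessment of concurrent use with contraindicated medications will also include drugs that were prescribed during the days' supply of the domperidone prescription". Item e of composite versions 3 and 4 in Section 9.7 carries this over, counting co-medication "prescribed within the days potentially covered by the domperidone prescription".

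The dates are fixed elsewhere:

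- Section 9.2.1: "Patients will be followed from the index date to the earliest of the following dates". The first date listed is the end of the study period.
- Section 9.2.2: the last part of the study period is "A 1-year post-implementation period of risk minimisation measures (1 October 2014 through 30 September 2015").
- Section 6: data collection ends "When data through SEP2015 become available for analysis (estimated as 4Q2016").

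The component is reported in its own right. Section 8.2 asks for proportions "for each of the components of the composite endpoint individually". Section 9.7 says "each of the above label requirements that contribute to the primary endpoint will be compared for the same two 1-year periods", and rates are to be shown "using quarterly time blocks for the pre- and post- risk minimisation implementation periods".

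**The concern.** One date, 30 September 2015, serves both as the last day for a post-period domperidone prescription and as the last day of data. A prescription written d days before it has at most d days in which a later contraindicated drug can be seen. One written on the day itself has none. The pre-period does not have this problem: its last prescriptions date from 31 March 2014, and tracked data continue for 18 months. Transfer out of a practice, or loss of up-to-standard status, can shorten follow-up in either period, but the administrative cut falls on one side only.

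The missed co-prescriptions lower the post-period rate of something the revised label contraindicates. The error therefore points towards success of the risk minimisation measures. It is most visible in the last quarterly block, where it can look like a late fall in concurrent use.

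**Working it through.** The protocol gives no figure to reproduce here. The size follows from its dates plus stated assumptions.

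**Inputs from the protocol.** Post-period of 365 days ending 30 September 2015 (9.2.2). Final quarter, July-September 2015, of 92 days. Data end 30 September 2015 (6, 9.2.1). Smallest database about 22,000 prescriptions (Belgium, 9.5), taken here as the number per period.

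**Assumptions, because the protocol gives no values.** Days' supply d of 7, 30 or 90. Domperidone prescriptions uniform over time. Co-prescriptions spread over days 1 to d after the domperidone date, either evenly or falling linearly.

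**Share of the forward increment lost.** A co-prescription on day k is missed if fewer than k days of data remain. With prescriptions uniform over T days this has probability k/T, so the share lost is L = E[k]/T.

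- Even spread: E[k] = (d+1)/2, which is 4, 15.5 and 45.5 days.
- Linearly falling: E[k] = (d+2)/3, which is 3, 10.67 and 30.67 days.

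| Days' supply | Year, even (T=365) | Quarter, even (T=92) | Year, falling | Quarter, falling |
|---|---|---|---|---|
| 7 | 4/365 = 1.10% | 4/92 = 4.35% | 0.82% | 3.26% |
| 30 | 15.5/365 = 4.25% | 15.5/92 = 16.85% | 2.92% | 11.59% |
| 90 | 45.5/365 = 12.47% | 45.5/92 = 49.46% | 8.40% | 33.33% |

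Each row applies only to prescriptions with that supply. The pre-period loss is 0 in every row.

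**Effect on the component.** If b is the share with a contraindicated drug current at prescription and f the forward increment, the post-period rate reads b + f(1 − L). Take b = 5%, f = 3% and no true change, so that the correct value is 8.00% in both periods (even spread):

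| Days' supply | Year reads | Post/pre ratio | Last quarter reads |
|---|---|---|---|
| 7 | 7.97% | 0.996 | 7.87% |
| 30 | 7.87% | 0.984 | 7.49% |
| 90 | 7.63% | 0.953 | 6.52% |

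For f from 1% to 5%, the one-year bias is f × L: 0.04 to 0.21 points at 30 days and 0.12 to 0.62 points at 90 days.

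**Comparison with sampling error.** With independent prescriptions, the SE of the difference is sqrt(2 × 0.08 × 0.92 / 22,000) = 0.26 points. At 30 days' supply the bias is below one SE. At 90 days with f = 3% it is 3 × 0.1247 = 0.37 points, which exceeds it.

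**Effect on the composite.** Versions 1 and 2 consider only co-medication prescribed on or before the domperidone date, so the artefact is exactly 1. In versions 3 and 4 any supply over 7 days already fails, so only windows of up to 7 days matter. With a forward rate f of 1% to 10%, the compliance ratio (post over pre) is (1 − f(1 − 0.011))/(1 − f) = 1.0001 to 1.0012.

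**The case against.** The strongest objection is size. The primary composite is essentially untouched. What remains is one secondary, descriptive component, under one of two scenarios that are meant only to bracket an unknown truth. This stands, and it limits how much weight the point can carry.

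The larger figures also depend on assumptions. They need long supplies, and the worked example holds f at 3% for every supply length, although a longer window should collect more co-prescriptions. That makes the 7-day figure too high and the 90-day figure possibly too low. If the prescription date counts as the first day of supply, E[k] becomes d/2 and the yearly losses fall slightly, to 1.0%, 4.1% and 12.3%. If the new label shortened post-period supplies, the cut shrinks further. All this is fair: the figures are a range and do not predict the actual size. The SE above treats prescriptions as independent, and repeat prescriptions in the same patient would probably widen it.

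Two readings of the text would weaken the point. Section 9.2.1 speaks of study periods in the plural just before the follow-up rule. If follow-up ended with each one-year period, both years would be cut alike. Section 9.2.2, however, uses the singular term for the whole span to 30 September 2015. Section 9.7 once ends the post-period on 31 March 2015, which would leave room to look forward, but the same sentence calls it a one-year period, and the abstract, 8.1 and 9.2.2 all give 30 September 2015.

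It may also be said that incomplete windows belong in the statistical analysis plan, or that Section 9.9.2 covers the matter. An analysis plan cannot recover records that the protocol's data end leaves out. Section 9.9.2 concerns unknown treatment length and does not mention a cut affecting one period only.

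**Conclusion.** The concern holds as a small, one-sided bias fixed by the protocol's own dates. It is confined to the scenario-2 concurrent-use component and its quarterly series, and always favours apparent improvement. Over the year it is minor unless long supplies are common. In the July-September 2015 block it can be large enough to be misread as a trend. The direction rests on reading the study period as the whole span to 30 September 2015. The size rests on the assumed supply length, forward increment and timing of co-prescriptions. The case for changing the plan is that the bias is avoidable at almost no cost, not that any primary result is threatened.

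**What to change.** In Sections 9.2.1 and 6, keep 30 September 2015 as the last date for domperidone prescriptions, but run follow-up and extraction of co-medication records to 31 December 2015. Those 92 extra days remove the administrative cut for any supply up to 90 days. At 120 days the remaining loss is (1 + 2 + … + 28)/(120 × 365) = 406/43,800 = 0.9%.

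The cost is one changed extraction date. Annex 5 puts the availability of December 2015 data at the end of January 2016 for CPRD and Belgium and the end of February 2016 for Germany. The French and Spanish databases are updated monthly. The data milestone is 4Q2016.

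If the extension is impossible, compute the scenario-2 component without any prescription written from 1 July to 30 September 2015, whatever its supply. Leave out 1 July to 30 September 2013 as well, so that both periods keep the same nine calendar months. Flag the July-September 2015 quarterly rate as incompletely observed. This is clearly second best. It keeps 273/365 = 75% of the days (about 16,500 of Belgium's 22,000 prescriptions if uniform), widens the SE by sqrt(365/273) = 1.16, and departs from the commitment in Section 9.5 to analyse all eligible prescriptions. A bias this small would not justify that loss if the extension were available.

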9.3.6. A Composite Endpoint -All Label Requirements

Each prescription will be classified according to whether it appears to violate at least 1 of the above specifications, i.e., has a presumed indication that is off-label, has a dose that is above 30 mg/day (for ages \geq 12 years) or above 0.75 mg/kg/day (for ages <12 years), is written for a patient with a contraindicated condition, or appears to be prescribed concurrently with a medication contraindicated for concurrent use.

To accommodate the 2 areas of uncertainty described above (1] duration of domperidone use and 2] domperidone prescriptions for which the indication is unknown), the above classification will be done in the following 4 ways to reflect the possible combinations of:

- With consideration of days' supply being more than 7 days;
- Without consideration of days' supply being more than 7 days;
- With classifying subjects with an unknown indication as having an off-label indication; and
- Without classifying subjects with an unknown indication as having an off-label indication

This is described in more detail in Section 9.7.

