4. ABSTRACT

Title of Study

A Drug Utilisation Study of Domperidone in Europe Using Databases

Rationale and Background

In March 2013, the European Medicines Agency (EMA) Pharmacovigilance Risk Assessment Committee (PRAC) initiated a review of domperidone-containing medicines at the request of the Federal Agency for Medicines and Health Products (FAMHP), under Article 31 of Directive 2001/83/EC over concerns about cardiac adverse effects of domperidone. Subsequently, PRAC recommended that the product label (Summary of Product Characteristics/SmPC and Patient Information Leaflet/PIL) of domperidone-containing medicines be updated to strengthen the information regarding cardiac risks. In addition, PRAC raised concerns that there may be off-label use of domperidone for the stimulation of lactation in breastfeeding women, for the treatment of gastro-oesophageal reflux disease (GERD), for the treatment of diabetic and non-diabetic gastroparesis, and for the treatment of symptoms of postural hypotension in Parkinson's patients. More recently the EMA asked that inflammatory bowel syndrome (IBS) be included in the present study as an off-label indication.

The recommended changes following conclusion of the Article 31 referral included the following:

- restriction of the indication to nausea and vomiting;
- limitation of duration of use to 7 days;
- reduction of the maximum daily dose to 10 mg TID for adults and adolescents (12 years of age and older and weighing 35 kg or more);
- reduction of the maximum daily dose to 0.25 mg/kg TID for neonates, infants, children (less than 12 years of age), and adolescents weighing less than 35 kg;
- contraindication of the combination with other drugs that increase the cardiac risks by themselves or increase the plasma level of domperidone; and
- contraindication in patients with moderate or severe hepatic impairment or certain cardiac conditions.

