7.2. Background

In 2011, the EU Pharmacovigilance Working Party (PhVWP) recommended that the product information for domperidone-containing medicines should be updated to reflect the risk of adverse cardiac effects of domperidone including QT prolongation, arrhythmias, and sudden cardiac death, and that domperidone should be used with caution in patients with certain heart conditions, including heart failure, a previous heart attack, angina (chest pains), and heart rhythm disorders. In response to this recommendation, the SmPC was updated in 2012 to include QT prolongation as an adverse drug reaction (ADR).

In March 2013, the EMA PRAC initiated a review of domperidone-containing medicines at the request of the Federal Agency for Medicines and Health Products (FAMHP), under Article 31 of Directive 2001/83/EC over concerns about cardiac adverse effects of domperidone. Subsequently, PRAC recommended that the product label (Summary of Product Characteristics/SmPC and Patient Information Leaflet/PIL) of domperidone-containing medicines should be updated to strengthen the information regarding cardiac risks. In addition, PRAC raised concerns that there may be off-label use of domperidone for the stimulation of lactation in breastfeeding women, for the treatment of

gastro-oesophageal reflux disease (GERD), for the treatment of diabetic and non-diabetic gastroparesis, and for the treatment of symptoms of postural hypotension in Parkinson's patients. More recently the EMA asked that IBS be included in the present study as an off-label indication.

The recommended changes following conclusion of the Article 31 referral included the following:

- restriction of the indication to nausea and vomiting;
- limitation of duration of use to 7 days;
- reduction of the maximum daily dose to 10 mg TID for adults and adolescents (12 years of age and older and weighing 35 kg or more);
- reduction of the maximum daily dose to 0.25 mg/kg TID for neonates, infants, children (less than 12 years of age), and adolescents weighing less than 35 kg;
- contraindication of the combination with other drugs that increase the cardiac risks by themselves or increase the plasma level of domperidone; and
- contraindication in patients with moderate or severe hepatic impairment or certain cardiac conditions.

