9.3.3. Dose per Day

Dose per day will be described as dose in mg/day for subjects ≥ 12 years of age and in mg/kg/day for subjects < 12 years of age (if weight information is available for up to 1 year prior to the prescription). Exceeding the maximum daily dose of 30 mg for adults and 0.25 mg/kg TID for children will be evaluated.

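### The composite endpoint sets its dose limit by age alone, so 10 mg three times daily passes in an adolescent under 35 kg whose label limit is below 26.25 mg/day

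*Protocol*

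**What the plan says.** The abstract and Section 7.2 list the label changes that followed the Article 31 referral. The abstract gives the higher dose limit as "10 mg TID for adults and adolescents (12 years of age and older and weighing 35 kg or more"). In Section 7.2 the group held to 0.25 mg/kg three times daily consists of neonates, infants, children under 12, "and adolescents weighing less than 35 kg". From age 12 the limit for an adolescent therefore depends on weight.

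Section 9.3.6 defines the composite of all label requirements. From age 12 a prescription fails on dose only if it "has a dose that is above 30 mg/day"; under age 12 it fails above 0.75 mg/kg/day. Weight does not decide which rule applies.

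Section 9.3.3 describes dose in mg/day from age 12 and in mg/kg/day below that age, "if weight information is available for up to 1 year prior to the prescription". It then says: "Exceeding the maximum daily dose of 30 mg for adults and 0.25 mg/kg TID for children will be evaluated". Section 9.7 lists the dose condition in all four versions of the composite simply as "Dose no higher than recommended".

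**The concern.** The endpoint is meant to measure compliance with the revised label, yet its numeric dose rule differs from the label that the same protocol records. A programmer who follows Section 9.3.6 will pass every prescription of up to 30 mg/day from age 12, including those above the limit for an adolescent under 35 kg. Doses above 30 mg/day are still caught. The error can only make compliance look better.

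The four versions of the composite do not bracket it. They vary the handling of unknown indication and of duration, and the dose condition is the same in each, including the most pessimistic one.

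The place where it could show is the dose component, because Section 9.7 says that "each of the above label requirements that contribute to the primary endpoint will be compared for the same two 1-year periods". It could also enter the paediatric results, since "Paediatric data will be described separately from adult patients", although no separate adolescent stratum is stated.

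**Working it through.** **Reproducing the plan's cut-offs.** From the label in the abstract and Section 7.2:

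- 3 × 10 mg = 30 mg/day
- 3 × 0.25 mg/kg = 0.75 mg/kg/day

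Both match Section 9.3.6. The numbers are right; the group each one applies to is not.

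**One prescription of 10 mg three times daily, patient aged 12 or older.** The label limit under 35 kg is 0.75 × weight.

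| Weight (kg) | Label limit (mg/day) | 30 ÷ limit | Label | Section 9.3.6 |
|---|---|---|---|---|
| 25 | 18.75 | 1.60 | exceeds | passes |
| 30 | 22.5 | 1.33 | exceeds | passes |
| 34 | 25.5 | 1.18 | exceeds | passes |
| just under 35 | just under 26.25 | just over 1.14 | exceeds | passes |
| 35 or more | 30 | 1.00 | within | passes |

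Below 20 ÷ 0.75 = 26.7 kg, 20 mg/day also exceeds the label limit and passes.

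**Whether another section repairs this.** Section 9.3.3 uses age 12 to choose the unit of description and names limits for adults and children without placing adolescents. The dose condition in Section 9.7 is compatible with the label but gives no rule. The limitations in Section 9.9.2 do not mention weight. The only explicit rule is the one in Section 9.3.6.

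**Effect on the results.** Let q be the share of all prescriptions that go to adolescents under 35 kg at doses above 0.75 mg/kg/day and up to 30 mg/day. The protocol gives no figure. I assume q = 0.0001 to 0.001, equal in both periods, and also show 0.01 as an extreme. Let p0 be true compliance before the label change, and take a true post/pre risk ratio of 1.10, the smallest in Table 2.

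- Dose component: compliance is overstated by q, that is 0.01 to 0.1 percentage points (1 point at the extreme).
- (a) The group passes the other components at rate p0 in both periods. Observed ratio = (1.1 + q)/(1 + q), for any p0.
- (b) The group always passes the other components. Observed ratio = (1.1·p0 + q)/(p0 + q).
- (c) The group's pass rate on the other components rises from p0 to 1.1·p0. Observed ratio = (1.1·p0 + 1.1·q·p0)/(p0 + q·p0) = 1.10, so there is no bias.

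| q | (a) | (b) p0 = 10% | (b) p0 = 50% |
|---|---|---|---|
| 0.0001 | 1.09999 | 1.0999 | 1.09998 |
| 0.001 | 1.0999 | 1.0990 | 1.0998 |
| 0.01 | 1.0990 | 1.0909 | 1.0980 |

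**How large the group would have to be.** For an observed ratio of 1.095, the wrongly compliant share s solves (1.1·p0 + s)/(p0 + s) = 1.095, so s = 0.005·p0/0.095 = 0.053·p0. In case (a), where s = q·p0, this means q = 5.3% of all prescriptions. Nothing in the protocol suggests a group of that size.

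**The case against.** The best defence is that age alone is a deliberate and reasonable simplification. The title page and Section 9.3.3 both speak of just two groups, adults and children. Even for the under-12s the mg/kg dose depends on a weight being available, and Annex 5 does not expressly list body weight for any of the five databases. The dose condition in Section 9.7 would also let an analysis plan apply the 35 kg criterion. The same rule operates in both periods, and if light adolescents improve in step with everyone else the risk ratio is not biased at all. Nothing shows that even one such prescription exists.

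A weight-dependent rule has drawbacks too. A weight up to a year old in a growing adolescent can produce a false violation. If weight recording differs between periods, the new rule could add a small differential error that the present rule does not have.

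Most of this stands as an argument about size, and it keeps the point minor. It does not remove the contradiction. The protocol never presents the age rule as a simplification, it states the cut-offs numerically under a heading that claims all label requirements, and it compares the dose component in its own right.

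**Conclusion.** The concern holds. Section 9.3.6 misclassifies as within dose any prescription above 0.75 mg/kg/day and up to 30 mg/day in an adolescent under 35 kg. At 30 mg/day the excess over the label is at least 14%, and this follows from the protocol's own numbers.

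The overall effect is probably negligible for the country-level risk ratio and very small for the dose component. That judgement rests on an assumed share of 0.01% to 0.1% of prescriptions, equal in both periods, and the protocol offers nothing to check it against. This is a correction worth making, not a threat to the primary result.

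**What to change.** In Section 9.3.6, and to match in Section 9.3.3:

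- Score a dose violation above 0.75 mg/kg/day for ages under 12 and for adolescents whose latest recorded weight in the year before the prescription is under 35 kg. State the adolescent age range, for example 12 to 17 years, since the protocol gives no upper age.
- Keep the limit of 30 mg/day for everyone else aged 12 or older, including adolescents with no recorded weight.
- Report the number of adolescents with missing weight and the number of adolescent prescriptions whose dose class changes under this rule, for each period and country.
- Add a sentence to Section 9.9.2 saying that missing or outdated weights leave some misclassification.

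The cost is a wording change in two sections, slight programming to extend the one-year weight window to adolescents, two counts and one sentence. The error is only partly removed, because adolescents without a weight stay under the present rule and outdated weights near 35 kg will produce some false violations. Reporting the counts by period would show whether weight recording shifted, and whether the issue matters at all.
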